3. OBJECTIVES AND ENDPOINTS

Table 3 Study objectives

Primary Objective:	Endpoint/Variable:
To describe safety profile of durvalumab in combination with platinum–etoposide as first-line treatment for patients with ES-SCLC and also as monotherapy maintenance treatment.	Incidence of grade ≥ 3 AEs Incidence of imAE

Secondary Objective:	Endpoint/Variable:
To describe effectiveness of durvalumab in combination with platinum–etoposide as first-line treatment for patients with ES-SCLC.	Progression Free Survival (PFS). PFS rate at 6 months and at 1 year (PFS6, PFS12). Objective Response Rate (ORR): using site investigator assessments according to RECIST 1.1. Duration of Response (DoR) DoR at 1 year (DoR12). Time to Treatment Discontinuation (TTD). Overall Survival (OS). The OS rate at 6, 12 and 18 months. Time to event endpoints measured as time from first Durvalumab dose.
To describe the impact of durvalumab in combination with platinum–etoposide as first-line treatment for patients with ES-SCLC on patients’ disease-related symptoms and Health Related Quality of Life (HRQoL) and (PROs).	Changes in vital signs, physical findings, and clinical laboratory results during and following study treatment administration Change from baseline in European Organisation for Research and Treatment of Cancer Quality of Life Questionnaire Core 30 items (EORTC QLQ-C30). Change from baseline in European Organisation for Research and Treatment of Cancer Quality of Life Questionnaire-Lung Cancer 13 (EORTC QLQ-LC13).
To describe health care resources use related to management of ES-SCLC patients treated with durvalumab in combination with platinum–etoposide as first-line treatment.	Changes from baseline in PRO-CTCAE. 
- Number and length of hospitalizations- Number of visits to oncology service- Number of emergency visits- Number of outpatient visits- Number of imaging tests- Number of biopsy-related procedures- Treatment dose, duration, number of cycles

Secondary Objective:	Endpoint/Variable:

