Patients who continue to receive benefit from their assigned treatment at the final DCO and database closure may continue to receive their assigned treatment for as long as they and their physician considers they are gaining clinical benefit. Different drug supply options may be available and these will be proposed to the patient when the most appropriate alternatives for

continued treatment have been agreed between AZ and the Investigator. Options may include participation in a new rollover study, or if durvalumab has been locally approved for use in this disease indication, patients may be discontinued from study treatment and transitioned to the marketed product, in accordance with local laws. For patients continuing to receive durvalumab treatment following the final DCO and database closure, it is recommended that the patients continue the scheduled site visits and Investigators monitor the patients' safety laboratory results prior to and periodically during treatment with durvalumab in order to manage AEs in accordance with the durvalumab Dosing Modification and Toxicity Management Guidelines (see Section 8.4.5).

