6.3 Treatment compliance

Any change from the dosing schedule, dose delays/interruptions, dose reductions and dose discontinuations should be recorded in eCRF.

The Investigational Product Storage Manager is responsible for managing the IP from receipt by the study site until the destruction or return of all unused IP.

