7. DISCONTINUATION OF TREATMENT AND SUBJECT WITHDRAWAL

7.1 Discontinuation of study treatment

An individual patient will not receive any further durvalumab or EP dose if any of the following occur in the patient in question:

- Withdrawal of consent from further treatment with IP. The patient is, at any time, free to discontinue treatment, without prejudice to further treatment. A patient who discontinues treatment is normally expected to continue to participate in the study (eg, for safety and survival follow up) unless they specifically withdraw their consent to all further participation in any study procedures and assessments (see Section 7.3).
- An AE that, in the opinion of the Investigator or AstraZeneca, contraindicates further dosing
- Any AE that meets criteria for discontinuation as defined in the Dosing Modification and Toxicity Management Guidelines (see Section 8.4.5) or as defined in the local prescribing information for the EP treatment.
- Pregnancy or intent to become pregnant
- Non-compliance with the study protocol that, in the opinion of the Investigator or AstraZeneca, warrants withdrawal from treatment with IP (eg, refusal to adhere to scheduled visits)
- Initiation of alternative anticancer therapy including another investigational agent
- Clinical progression or confirmed radiological progression (refer to 0E) and Investigator determination that the patient is no longer benefiting from treatment with IP

- Completion of the study by the sponsor for obtaining the indication for ES-SCLC in combination with etoposide + platinum

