7.1.1 Procedures for discontinuation of study treatment

Discontinuation of study treatment, for any reason, does not impact the patient's participation in the study. A patient who decides to discontinue IP will always be asked about the reason(s) for discontinuation and the presence of any AE. The patient should continue attending subsequent study visits, and data collection should continue according to the study protocol. If the patient does not agree to continue in-person study visits, a modified follow-up must be arranged to ensure the collection of endpoints and safety information. This follow-up could be a telephone contact with the patient, a contact with a relative or treating physician, or information from medical records. The approach taken should be recorded in the medical records. A patient that agrees to modified follow-up is not considered to have withdrawn consent or to have withdrawn from the study.

Patients who are permanently discontinued from further receipt of IP, regardless of the reason, will be identified as having permanently discontinued treatment. Patients who are permanently discontinued will enter follow-up (see the SoAs).

Patients who permanently discontinue drug for reasons other than objective RECIST disease progression should continue to have RECIST scans performed according usual clinical practice, at least q12w \pm 1w (relative to the date of inclusion), until RECIST 1.1-defined radiological PD plus an additional follow-up scan or death (whichever comes first) as defined the SoAs.

If a patient is discontinued for RECIST 1.1-defined progression, then the patient should have 1 additional follow-up scan performed preferably at the next (and no later than the next) scheduled imaging visit, and no less than 4 weeks after the prior assessment of PD.

All patients will be followed for survival until the end of the study.

Patients who decline to return to the site for evaluations should be contacted by telephone as indicated in the SoAs as an alternative.

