Any patient not known to have died at the time of analysis will be censored based on the last recorded date on which the patient was known to be alive. It will be analysed OS, OS at 6 months (6mOS) and OS at 12 months (12mOS) and OS at 18 months (18mOS).

- Time to Treatment Discontinuation (TTD): This analysis will be performed for the Intention-to-Treat population (ITT). TTD is defined as the time from the first date of treatment until date of discontinuation of treatment. Date of discontinuation will be the date reported in end of study form. It will be performed just on the patients that report treatment discontinuation, determined if any of the following occurs:
  - Withdrawal of consent from further treatment with IP.
  - An AE that, in the opinion of the Investigator or AstraZeneca, contraindicates further dosing.
  - Any AE that meets criteria for discontinuation as defined in the Dosing Modification and Toxicity Management Guidelines or as defined in the local prescribing information for the EP treatment.
  - Pregnancy or intent to become pregnant.
  - Non-compliance with the study protocol.
  - Initiation of alternative anticancer therapy including another investigational agent.
  - Clinical progression or confirmed radiological progression and Investigator determination that the patient is no longer benefiting from treatment with IP.

#### 4.2.2.2 Secondary outcome 2

To describe the impact of durvalumab in combination with platinum–etoposide as first-line treatment for patients with ES-SCLC on patients' disease-related symptoms and Health Related Quality of Life (HRQoL) and (PROs).

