- Overall survival (OS): OS will be analyzed using a Kaplan-Meier plots. Summaries of the number and percentage of patients who have died, those still in survival follow-up, those lost to follow-up, and those who have withdrawn consent will be provided along with the median OS and corresponding 95% CI. In addition, the survival rate at 6 (OS 6), 12 (OS 12), and 18 (OS 18) months will be presented.

A subgroup analysis may be conducted comparing OS in the following subgroups, assuming sufficient sample size per subgroup: platinum therapy receiving (carboplatin or cisplatin), age ( $\geq 65$ ,  $< 65$ ), gender, performance status, smoking status, CNS metastasis at baseline (Yes/No) and number of chemotherapy cycles (5 or 6 cycles vs 4 or less cycles)

For each subgroup, the HR and 95% CI will be calculated by Cox regression and a log-rank test will be provided.

- Time to Treatment Discontinuation (TTD): Summaries for the TTD will be provided (continuous data).

### 5.2.2 Secondary outcome 2

To describe the impact of durvalumab in combination with platinum–etoposide as first-line treatment for patients with ES-SCLC on patients' disease-related symptoms and Health Related Quality of Life (HRQoL) and (PROs).

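### TTD is summarised only in patients who have stopped treatment and has no censoring rule, so patients still on durvalumab are dropped and TTD is biased short

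*SAP*

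**What the plan says.** SAP 4.2.2.1 assigns TTD to the ITT population, which SAP 3.1 defines as enrolled patients with at least one dose. It defines TTD as running from first treatment to discontinuation, then limits the analysis: "It will be performed just on the patients that report treatment discontinuation, determined if any of the following occurs". A list of reasons follows. On the date it says: "Date of discontinuation will be the date reported in end of study form".

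SAP 5.2.1 gives the whole method for TTD: "Summaries for the TTD will be provided (continuous data". Under SAP 5 a continuous summary means n, mean, SD, median, quartiles and range. PFS, duration of response and OS each get a censoring rule in SAP 4.2.2.1 and Kaplan-Meier in SAP 5.2.1. TTD gets neither.

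Protocol section 3 lists TTD among the effectiveness endpoints and closes that list with "Time to event endpoints measured as time from first Durvalumab dose". Protocol 9.3 assigns TTD to the full safety analysis set. Protocol 9.4 gives TTD no censoring rule, and the table of planned analyses in 9.5.2.2 omits it.

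Protocol 6.1.3 provides for patients still on treatment at the end: "Patients who continue to receive benefit from their assigned treatment at the final DCO and database closure may continue". Section 6.6 continues drug supply after the final analysis, and section 8.1.2 has patients on treatment contacted after the data cutoff.

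**The concern.** A patient still on durvalumab at the cutoff has no discontinuation date. The correct information about that patient is that TTD exceeds the time observed so far. The SAP discards this and keeps only patients in whom the event has occurred, so it selects on the outcome. The patients lost are those who stayed on treatment longest relative to their follow-up. The reported TTD would then describe early and middle stoppers, not the treated population, and it would change with the cutoff date even if the drug were used identically.

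Two further points in the same SAP paragraph need clarifying.

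- **Reasons list.** It does not name death on treatment. It also omits the last reason in Protocol 7.1, "Completion of the study by the sponsor for obtaining the indication for ES-SCLC". How these patients are handled is therefore unclear.
- **Date source.** If the end of study form records the end of participation and not the treatment stop, TTD would be too long, because discontinued patients stay under observation: "All patients will be followed for survival until the end of the study". This depends on the eCRF, which is not among the documents.

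**Working it through.** The plan states no TTD figure, so there is nothing of its own to reproduce.

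**Direction.** Let T be the true time on treatment and C the patient's follow-up at the cutoff, independent of T. The SAP analyses T only where T ≤ C. That conditional distribution is shorter than T's whenever some patients have T > C, whatever the shape of T.

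**Inputs for the size**

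- N about 85, accrual 6 months (SAP 2.1, 2.2).
- Enrolment Q4 2020 to Q2 2021, last patient completed Q2 2022 (Protocol 1.2): about 12 months of follow-up for the last patient and 18 for the first.
- Median TTD M: not given. Assumed 4 to 8 months. The only related figure is a median time to progression of 4 to 6 months on chemotherapy (Protocol 2.3.3).
- Shape: assumed exponential, with C uniform on (a, b).

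**Formulas**, with λ = ln 2 / M:

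- Share still on treatment: p = (e^(−λa) − e^(−λb)) / (λ(b − a)).
- Median among discontinuers, m: 1 − e^(−λm) = ½(1 − p), so m = −ln(½ + p/2)/λ. This is valid because m < a in every case below.

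**Worked case**, M = 6, follow-up 12 to 18 months:

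- λ = 0.1155, e^(−12λ) = 0.25, e^(−18λ) = 0.125.
- p = 0.125/0.693 = 0.180, and 85 × 0.180 ≈ 15 patients dropped.
- m = −ln(0.590)/0.1155 ≈ 4.56 months, and 4.56/6 = 0.76, so 24% too short.

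**Results** (share dropped; median reported; bias):

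| Follow-up | True median 4 mo | True median 6 mo | True median 8 mo |
|---|---|---|---|
| 12–18 mo (planned dates) | 7.8%; 3.57; −11% | 18.0%; 4.56; −24% | 27.6%; 5.19; −35% |
| 18–24 mo | 2.7%; 3.84; −4% | 9.0%; 5.25; −12% | 16.4%; 6.25; −22% |
| 9–15 mo | 13.1%; 3.29; −18% | 25.5%; 4.03; −33% | 35.8%; 4.47; −44% |

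In the planned window the numbers dropped are about 7, 15 and 23 of 85. The mean, which the SAP also reports, is affected more: about 4.6, 5.4 and 5.9 months among discontinuers, against true means of 5.8, 8.7 and 11.5.

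**Shape sensitivity.** Suppose 15% to 25% of patients belong to a long-duration subgroup with a median of 36 months (assumed), with the overall medians still 4 to 8 and follow-up 12 to 18 months. Then 15% to 31% are dropped and the reported median is 21% to 42% too short.

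**Check of the remedy.** In 4,000 simulated trials of 85 patients with 12 to 18 months of follow-up, Kaplan-Meier in all patients gave average medians of 5.05, 6.04 and 8.07 for true values of 5, 6 and 8. The SAP rule gave 4.16, 4.59 and 5.21.

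**The case against.** The restriction and the missing censoring rule are plain in the text. The arguments on the other side concern how much they matter.

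- **The net direction is not certain.** A late date from the end of study form, or early deaths left out, would lengthen TTD. This stands as far as it goes: the restriction itself shortens TTD, and the other two effects depend on the eCRF and on how the SAP is read. Possible offsetting errors of unknown size are not a defence.
- **Other text softens it.** SAP 5 reports missing counts and reasons for non-evaluability, so the number left out may be visible. SAP 4.3.4 describes duration of treatment by phase in the ITT population. The synopsis promises Kaplan-Meier curves for time-to-event outcomes. None of this cures the problem. A visible count does not correct a biased median, the duration summaries give no rule for patients still on treatment, and the synopsis sentence names only OS and PFS while the SAP sets a different method for TTD.
- **The size rests on assumptions.** This is correct. Within the 4 to 6 month anchor the bias is 11% to 24% (12 to 18 months) or 4% to 12% (18 to 24 months), and the planned 18-month OS rate makes the longer window plausible. The sampling half-width of a median at N = 85 is about 1.96/(ln 2 × √85) = 31% of the median, larger than the bias in that range. But a bias is systematic, and a confidence interval around the wrong quantity does not reveal it.
- **Nothing is tested.** TTD is one descriptive secondary endpoint in a study without hypotheses. That limits the consequence, but a descriptive figure should still describe the patients treated.

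**Conclusion.** The concern holds. As written, the SAP selects TTD patients on the outcome, contradicts its own ITT assignment, and departs from the protocol's treatment of TTD as a time-to-event endpoint in all treated patients. The restriction shortens TTD whenever anyone is still on durvalumab at the cutoff, given only that follow-up time is independent of time on treatment.

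The size depends on the unstated cutoff and TTD distribution. It is a few percent if nearly everyone has stopped, and about a quarter for a 6-month median with follow-up on the planned dates. It is more with longer treatment or an earlier cutoff. The handling of deaths, sponsor-completed stops and the date source remains open. This should be fixed, but it does not touch the primary safety objective.

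**What to change.** In SAP 4.2.2.1, delete the restriction to patients who report discontinuation. In SAP 5.2.1, replace the continuous summary with a Kaplan-Meier analysis in all treated patients, and state:

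- **Event:** permanent discontinuation of durvalumab, or death on treatment. Study treatment formally includes platinum and etoposide, so the choice of durvalumab should be explicit. It matches the protocol's time origin.
- **Censoring:** patients still on treatment, at the data cutoff. Patients who stop only because the sponsor completes the study, or who transfer to marketed product or a rollover study, at the date of stopping. Protocol 7.1 lists sponsor completion as a discontinuation reason, so the SAP should say that it is censored for this analysis.
- **Date:** the treatment-stop date from the dosing records, with the eCRF field named.
- **Report:** median, 95% CI and number still on treatment.

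The cost is SAP wording and one Kaplan-Meier table. No new data collection appears necessary, since Protocol 6.3 already says that "dose delays/interruptions, dose reductions and dose discontinuations should be recorded in eCRF".

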Time to event endpoints measured as time from first Durvalumab dose.
Changes in vital signs, physical findings, and clinical laboratory results during and following study treatment administration
Change from baseline in European Organisation for Research and Treatment of Cancer Quality of Life Questionnaire Core 30 items (EORTC QLQ-C30).
Change from baseline in European Organisation for Research and Treatment of Cancer Quality of Life Questionnaire-Lung Cancer 13 (EORTC QLQ-LC13).

To describe health care resources use related to management of ES-SCLC patients treated with durvalumab in combination with platinum–etoposide as first-line treatment.

Changes from baseline in PRO-CTCAE.

- Number and length of hospitalizations
- Number of visits to oncology service
- Number of emergency visits
- Number of outpatient visits
- Number of imaging tests
- Number of biopsy-related procedures
- Treatment dose, duration, number of cycles

[REDACTED]

[REDACTED]

[REDACTED]

Once the eligible participant has given the informed consent to be included at the program, study variables apart from those that will be used to assess the objectives, will include at least the following:

- **Demographic characteristics:** age, gender, race/ethnicity, smoking status, family history of cancer.
- **Clinical characteristics:** SCLC stage, tumor site and histology, number and location of metastases including brain metastases, presence of other primary malignancy at diagnosis, performance status according to the ECOG scale.

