6.6 Treatment after the end of the study

After the final analysis, AstraZeneca will continue to supply open-label drug to patients receiving durvalumab monotherapy up to the time that they discontinue the treatment for whatever reason (see Section 6.1.2).

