8.1.2 Survival assessments

Assessments for survival must be made every 2 months following treatment discontinuation. Survival information may be obtained via telephone contact with the patient or the patient's family, or by contact with the patient's current physician. The details of first and subsequent therapies for cancer, after discontinuation of treatment, will be collected.

In addition, patients on treatment or in survival follow-up will be contacted following the data cutoff for the primary analysis and all subsequent survival analyses to provide complete survival data. These contacts should generally occur within 7 days of the data cutoff.

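### Time to treatment discontinuation is summarised only in patients who have already stopped, with no censoring, so patients still on durvalumab at data cut-off are left out

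*SAP*

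**What the plan says.** SAP 4.2.2.1 names the ITT population (all treated patients) for TTD and defines it as the time from first treatment date to discontinuation date. It then restricts the analysis: "It will be performed just on the patients that report treatment discontinuation, determined if any of the following occurs". The seven reasons listed are withdrawal of consent to treatment, two adverse-event reasons, pregnancy, non-compliance, start of another anticancer therapy, and progression without further benefit. On the date, it says: "Date of discontinuation will be the date reported in end of study form". SAP 5.2.1 adds only that TTD will be summarised as continuous data. PFS, DoR and OS each have a censoring rule and a Kaplan-Meier analysis in the same SAP sections; TTD has neither.

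In the protocol, the list of effectiveness endpoints in section 3 that contains TTD closes with the note "Time to event endpoints measured as time from first Durvalumab dose", and the populations table in 9.3 gives TTD the full safety analysis set. Section 6.1.3 makes provision for "Patients who continue to receive benefit from their assigned treatment at the final DCO", and section 6.6 states that after the final analysis "AstraZeneca will continue to supply open-label drug to patients receiving durvalumab monotherapy up to the time that they discontinue the treatment". Section 7.1 has an eighth stopping reason, completion of the study by the sponsor, which the SAP list omits.

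**The concern.** An analysis limited to patients who have already had the event conditions on the outcome. Patients drop out of the TTD summary because they stayed on drug, and how many drop out depends on when the data are cut. The restriction also contradicts the ITT declaration in the same SAP paragraph and the population in protocol 9.3.

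Two further features act on the same number.

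- Death on treatment is not a listed reason. Some deaths may enter through the adverse-event or progression reasons; any that do not are lost, and these would tend to be short times.
- The stop date is read from a form about leaving the study, yet patients remain in the study after stopping drug. Protocol 7.1.1 says "All patients will be followed for survival until the end of the study", and 8.1.2 says "Assessments for survival must be made every 2 months following treatment discontinuation". If the form carries the study-exit date, every TTD is too long.

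At stake is a named secondary effectiveness endpoint. Its median would describe early stoppers under an ITT label and could not be read beside the censored PFS and OS estimates.

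**Working it through.** Neither document states a TTD figure, so there is none to reproduce. The calculation below shows what the written rule does under stated assumptions.

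**Inputs**

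- n = 85 (SAP 2.2).
- Follow-up C. The synopsis dates (first patient Q4 2020, last enrolled Q2 2021, last completed Q2 2022) suggest about 12 to 18 months, taken as uniform. Because an 18-month OS rate is planned, C = 18 months and C uniform on 18 to 24 months were also run.
- Time on durvalumab T: assumed exponential with median m. The documents give no value, so m = 4, 6, 8 and 10 months were used.

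**Restriction alone**

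Share still on drug, hence excluded: q = mean of 2^(−C/m). Reported median t (when it lies below the shortest follow-up): solve 1 − 2^(−t/m) = (1 − q)/2.

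For m = 6 and C = 18: q = 2^(−3) = 12.5%. Then 2^(−t/6) = 1 − 0.4375 = 0.5625, so t = −6·log2(0.5625) = 4.98 months.

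For m = 6 and C uniform on 12 to 18: q = (2^(−2) − 2^(−3))/ln 2 = 0.125/0.693 = 18.0%. Then 2^(−t/6) = 1 − 0.410 = 0.590, so t = 4.56 months.

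Simulation with 4 million draws gives the full set (excluded %; reported median in months):

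| True median | C 12–18 | C = 18 | C 18–24 |
|---|---|---|---|
| 4 | 7.8%; 3.57 | 4.4%; 3.75 | 2.7%; 3.84 |
| 6 | 18.0%; 4.56 | 12.5%; 4.98 | 9.0%; 5.25 |
| 8 | 27.6%; 5.19 | 21.0%; 5.79 | 16.4%; 6.24 |
| 10 | 35.6%; 5.61 | 28.7%; 6.36 | 23.5%; 6.95 |

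At m = 6 the exclusions are about 15, 11 and 8 of 85 patients, and the median is about 24%, 17% and 12% too short. At m = 4 it is about 11%, 6% and 4% too short, for example (4 − 3.57)/4 = 10.8%.

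In 3,000 simulated trials of 85 patients at m = 6, the stoppers-only median averaged 4.60, 5.03 and 5.28 months. Kaplan-Meier with censoring gave 6.07, 6.06 and 6.04.

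**Opposing effects, m = 6** (follow-up in the same order)

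- *Unlisted early deaths.* Assumed uniform over the first 3 months, with the overall median held at 6. If 5% of patients are lost this way, the reported median is 4.74, 5.21 and 5.52; if 10%, it is 4.94, 5.46 and 5.83. These stay below 6.
- *Study-exit date used.* Recorded date = min(T + G, C), with G an exponential gap between stopping drug and leaving the study. A mean gap of 2 months gives 6.68, 7.12 and 7.41, now too long. The shortening is exactly cancelled by a mean gap of 1.35, 0.96 or 0.72 months. At m = 4 the cancelling gap is 0.42, 0.24 or 0.15 months.

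**The case against.** The strongest reply is that the harm is limited and the gap did not begin in the SAP.

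- The protocol's table of planned analyses in 9.5.2.2 omits TTD, and the protocol gives TTD no definition or censoring rule. The note about time-to-event endpoints fixes a time origin, not a method. This is true. But the synopsis plans Kaplan-Meier curves for time-to-event outcomes, and 9.3 assigns TTD to all treated patients, so the SAP restriction still departs from the protocol on population.
- SAP sections 5 and 6.2 require missing counts for every analysed variable, and section 5 also requires reasons for non-evaluability. A reader should therefore see how many patients lack a TTD value. SAP 4.3.4 also reports treatment duration by phase, the number with 12 or more durvalumab doses in the chemotherapy phase, and the number with 12 or more post-chemotherapy cycles. These outputs show that long-treated patients exist. They do not correct the TTD median, and the phase durations have no censoring rule either.
- Protocol 2.3.3 cites a median time to progression of 4 to 6 months in this disease. If time on durvalumab is near 4 months, the shortening is 0.2 to 0.4 months. That stands as a limit on size. It is a figure for progression in the disease generally, not for time on durvalumab.
- The exit-date effect depends on a form that is not among the documents. This also stands, and it is why no net direction is claimed.
- TTD is descriptive and secondary, and the primary safety analysis, PFS and OS are unaffected. That bears on priority, not on whether the rule is right.

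**Conclusion.** The concern holds. Followed as written, the SAP excludes from TTD every patient still on durvalumab at cut-off, together with those whose treatment ends because the sponsor completes the study. The direction of the restriction taken alone is certain: it shortens the reported time.

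Its size is illustrative and rests on exponential times on treatment and assumed follow-up. Across true medians of 4 to 10 months, the reported median would be 3.6 to 5.6 months with 12 to 18 months of follow-up, and 3.8 to 7.0 months with 18 to 24. The handling of deaths and the source of the date can offset or reverse this by an unknown amount, so the net direction is not established. The defect should be corrected before the final analysis. It does not touch the primary endpoint.

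**What to change.** Amend SAP 4.2.2.1 and 5.2.1 so that:

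- TTD is analysed by Kaplan-Meier in all treated patients, with the median and its 95% CI.
- The event is permanent discontinuation of durvalumab for any of the seven listed reasons, or death on treatment. State explicitly that the event refers to durvalumab, because study treatment also includes etoposide and platinum.
- Patients still on durvalumab at data cut-off, patients stopped because the sponsor completes the study (last item of protocol 7.1), and patients moved to another source of supply are censored at their last on-study durvalumab dose. The simulated check above censored at study end; last-dose censoring would normally fall within about one cycle of it.
- The discontinuation date comes from the dosing records that protocol 6.3 already requires in the eCRF, not from the end of study form.

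The cost is one SAP amendment before the final analysis. It needs no protocol change and no new data.
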